3.0 Objectives

- **Describe the study's purpose, specific aims, or objectives.**

The specific aims are:

1) To conduct a randomized controlled trial among PC survivors with high symptom burden comparing the impact of this personalized intervention for improving symptoms and symptom self-management to nonpersonalized information. We hypothesize that relative to controls, 5- and 12- months post-enrollment, Veterans in the intervention group will: 1) have higher confidence about symptom self-management; and 2) report lower symptom burden and better disease-specific QOL. We further hypothesize that at the 12-month assessment point, the intervention group will have higher scores on two key psychosocial indicators (subjective health and perceived cancer control) than the control group.

2) To determine the intervention's impact on the use of primary and specialty VA services. We hypothesize that relative to controls, 12 months after enrollment, Veterans in the intervention group will have a higher rate of symptom-specific service use that is consistent with Michigan Cancer Consortium recommendations for prostate cancer survivorship care, which are expert and evidence-based. This project could have a significant positive impact on the lives of the large and growing population of Veterans who are PC survivors experiencing post-treatment symptoms. Data from our preliminary work suggest that many of these survivors continue to suffer with high symptom burden years after treatment, report wanting to participate in self-management interventions, and that an automated telephone system is feasible and potentially effective. Our team has extensive expertise in the development and deployment of highly personalized, automated interventions for improving self-management in the VA, as well as the clinical and health services research expertise to successfully implement and complete the study. We have the support of the Office of Specialty Care/Patient Care Services as well as the VA Ann Arbor PACT (Patient Aligned Care Team) Laboratory. To ensure that the trial has the greatest possible impact on VA care, we will conduct a process evaluation to determine how the intervention can best optimize the quality of life and survivorship care for Veterans with prostate cancer and inform program implementation with our primary care partners.

- **State the hypotheses to be tested.**

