There are three primary Veteran-reported trial outcomes which will be measured at 5- and 12-months post enrollment: 1) confidence in symptom self-management, 2) implementation of symptom self-management, and 3) symptom burden and PC-QOL. Self-efficacy in patient-physician interactions will also be assessed at baseline, 5-months and 12-months. Participants in the trial will be randomized by computer by VA Ann Arbor Healthcare System (VAAHS) study staff. We hypothesize better outcomes in the intervention arm relative to enhanced usual care. The impact of the intervention on two secondary psychosocial outcomes, overall subjective health and perceptions of cancer control, will be assessed only at the 12-month time point, when we believe the intervention is most likely to have had its impact on these outcomes. The trial will be conducted in four VA sites (Ann Arbor, Cleveland, Pittsburgh, and St. Louis) with a large and racial/ethnically diverse population of PC survivors between 1-10 years post-treatment. The intervention is based on a conceptual framework that describes how self-management contributes to positive outcomes for cancer patients and survivors; we also will utilize theoretical constructs from patient empowerment and cognitive behavioral therapy (CBT) to inform the content of our intervention. We will compare the quality of health care received in intervention and control subjects using guidelines for prostate cancer survivorship care developed by the Michigan Cancer Consortium as a benchmark. Finally, we will prepare for implementation of the intervention on a broader scale through a formative evaluation. This design will allow us to understand how the intervention can best optimize the quality of life and quality of care for Veterans with PC, and will inform how to implement the program more broadly with our primary care partners.

- **Include a description of how anticipated risk will be minimized and include an analysis of risk vs. potential benefit.**

How anticipated risk will be minimized:

Veteran participants:

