We will use the Expanded Prostate Cancer Index (EPIC) to assess PC-symptom burden and associated PC-QOL at the baseline, 5- and 12-month assessments. The EPIC was developed by our study consultant, [name], and has been widely used in prostate cancer survivorship research. The EPIC is a 26-item measure that assesses symptom burden in four domains: urinary symptoms (9 items), bowel symptoms (6 items), sexual symptoms (6 items) and vitality (5 items). Each domain has a subscale related to function and bother which together contribute to disease specific quality of life. Prior work by [name] and colleagues has shown that these domains have good internal consistency (Chronbach's alpha > 0.82 for each domain) and correlate highly with other established measures of QOL.¹⁰⁷ Each domain has a range of possible scores from 0 to 100, with lower scores indicating worse symptom burden. Lower EPIC scores for any one domain are associated with lower function in that domain (e.g., lower sexual health function) and lower QOL. Thus higher symptom burden, which reflects both function and bother scores, translate into lower EPIC scores. Based on consultation with [name] and on prior work by his team, for purposes of this study we will consider a score of 70 or less to indicate "clinically meaningful symptom burden" for any one domain. We will conduct primary outcome analyses using the EPIC. Self-efficacy in patient-physician interactions will also be assessed both at baseline and 12-months using a 5-item short form version of the Perceived Efficacy in Patient-Physician Interactions (PEPPI). The PEPPI was developed to measure older patients' self-efficacy in obtaining medical information and attention to their medical concerns from physicians. PEPPI has good convergent and discriminant validity and strong reliability ($\alpha=0.93$).

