At the 12-month assessment we will evaluate two key psychosocial domains of QOL (subjective health and perceptions of cancer control) that have been shown to be impacted by PC treatment in prior research. We will assess subjective health using the VR-12, an established measure of overall QOL that includes perceptions of one's health. We will assess perceived cancer control using a measure developed in prior research examining the psychosocial impact of prostate cancer; this measure includes three domains related to confidence that one's cancer is under control, worries about recurrence, and appraisals of one's coping with prostate cancer. We will evaluate these

outcomes at the 12-month assessment because that is when we expect the intervention would have its largest impact on these psychosocial domains of QOL.

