Aim 1 outcome analyses: Our primary outcomes for Aim 1 will be changes in symptom burden and bother scores at 5-months relative to baseline, using the EPIC measure. We will also evaluate these outcomes at the 12-month assessment point, but focus on the 5-month for primary outcome assessment as it is closest to the completion of the intervention. Multiple regression analysis will be used to evaluate the primary outcomes. The model will include an indicator for intervention group as the primary independent variable, and treatment type indicator (surgery vs. radiotherapy) and study site indicators as covariates. Baseline variables found to differ between the two study groups in the baseline analysis will also be included as covariates, though we expect the groups to be balanced on demographic and symptom scores by the randomization process. The coefficient for the intervention group indicator will be used to evaluate the impact of the personalized automated prostate cancer symptom management program compared to standard information. For change in symptom burden, we will repeat the analysis using each of the four symptom domains for EPIC. We will use the same analytic approach to evaluate changes in confidence in symptom self-management, our second Aim 1 outcome. We hypothesize that for both Aim 1 outcomes, intervention group survivors will have better scores at both 5- and 12-month assessments relative to those in the group (i.e., less symptom burden and better PC-QOL, more confidence in symptom self-management). For patients with available data at both 5- and 12-months, we will assess the trajectory of symptoms over time. This will be done using a linear mixed-effects model with random effects for each subject, an indicator for intervention group, an indicator of follow-up wave (5 versus 12 months) and an interaction of time by intervention group to model potential changes in the intervention effect on symptoms soon (at 5-months) vs. long (at 12-months) after the intervention is discontinued. If the interaction is not significant, we will drop the interaction term from the model and estimate the time-averaged difference in outcomes between the two study groups. Analyses of other outcomes, such as self-management implementation and confidence, will be done similarly.

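### VR-12 and perceived cancer control appear to have no baseline score; the stated rationale covers skipping 5 months but not baseline, and the price is precision

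*Combined protocol and SAP*

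**What the plan says.** Section 3.0 (Objectives) states a hypothesis for 12 months: "the intervention group will have higher scores on two key psychosocial indicators (subjective health and perceived cancer control) than the control group". Section 5.1 (Study Design) classes both outcomes as secondary and says that the intervention's impact on them "will be assessed only at the 12-month time point", because that is when an effect is thought most likely.

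Section 5.5 (Study Evaluations) gives the same timing ("At the 12-month assessment we will evaluate two key psychosocial domains of QOL") and the same reason. It names the VR-12 for subjective health. For perceived cancer control it describes a measure from prior research: "this measure includes three domains related to confidence that one's cancer is under control, worries about recurrence, and appraisals of one's coping with prostate cancer". It mentions baseline for neither.

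Other instruments are treated differently. Section 5.5 uses EPIC "to assess PC-symptom burden and associated PC-QOL at the baseline, 5- and 12-month assessments", and both 5.1 and 5.5 name baseline for PEPPI. Section 5.5 also provides for a telephone survey of every participant before randomisation, but does not itemise its content.

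Section 5.6 (Data Analysis) gives no model, significance level or power specific to these two outcomes. After describing regression on change from baseline and a mixed model over 5 and 12 months, it adds: "Analyses of other outcomes, such as self-management implementation and confidence, will be done similarly".

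**The concern.** The rationale answers a different question from the one that the design raises. Expecting the largest effect at 12 months is a reason not to measure at 5 months. A pre-randomisation score is not taken to detect an effect. It is taken to remove between-person variation from the 12-month comparison, to adjust for chance imbalance, and to show whether men who leave differed at the start. A survey that could carry the items takes place anyway.

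The analysis plan also fits poorly. Neither change from baseline nor a mixed model over two follow-up waves can be run on a single 12-month score. Section 5.6 handles imbalance by comparing baseline variables between arms and adjusting for those that differ, and a scale not measured at baseline cannot enter that procedure.

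At stake are wider confidence intervals than necessary for two stated hypotheses, and no view of drop-out by starting level on the scales concerned.

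**Working it through.** **Inputs from section 5.6.** Target difference 0.33 SD; 90% power; α = 0.0125 (chosen for the four EPIC domains); correlation 0.5 between baseline and follow-up symptom scores; 15% attrition at each assessment; 550 enrolled; 397 completers.

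**Assumptions.** The plan gives no correlation for the VR-12 or cancer control, so r = 0.3 to 0.7 is used, with 0.5 borrowed from the symptom scores. It gives no α for these outcomes, so two-sided 0.05 is used, with smaller values as a sensitivity check. The 0.33 SD target is kept because section 5.6 also cites it for other interval-scale outcomes.

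**Step 1: reproduce the plan's figure.** Analysis of covariance, normal approximation:

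n per arm = 2(z₁₋α/₂ + z₁₋β)²(1 − r²)/d² = 2(2.498 + 1.282)² × 0.75/0.33² = 197.

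This matches the stated 197 per group (394 in total). Without the baseline term, the factor 0.75 becomes 1 and the same target needs 263 per arm. The trial's own sample size therefore relies on the baseline adjustment that these two outcomes appear to lack.

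**Step 2: completers.** 550 × 0.85² = 397.4, or 198.5 per arm. Expected loss is 1 − 0.85² = 27.8%.

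**Step 3: 12-month comparison with and without the own baseline.** Power = Φ[d/√(2(1 − r²)/198.5) − 1.96]. With no baseline, 0.33/√(2/198.5) = 3.288, and Φ(3.288 − 1.96) = 90.8%.

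| Own baseline | SE ratio √(1 − r²) | SE cut | Power, 0.33 SD | Detectable at 90% power |
|---|---|---|---|---|
| none | 1 | – | 90.8% | 0.325 SD |
| r = 0.3 | 0.954 | 4.6% | 93.1% | 0.310 SD |
| r = 0.5 | 0.866 | 13.4% | 96.7% | 0.282 SD |
| r = 0.7 | 0.714 | 28.6% | 99.6% | 0.232 SD |

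At r = 0.5 the 397 completers would carry the information of 397/0.75 = 529 unadjusted men.

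**Step 4: sensitivity to α.** At α = 0.025 (two outcomes, Bonferroni), power is 85.2% without a baseline and 94.0% with r = 0.5. At 0.0125 it is 78.5% and 90.3%. The plan sets neither level for these outcomes.

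**Step 5: why a covariate and not a change score.** In units of the 12-month variance, a change score has variance 2(1 − r): 1.4, 1.0 and 0.6 at r = 0.3, 0.5 and 0.7. Analysis of covariance gives 1 − r²: 0.91, 0.75 and 0.51. At r = 0.5 a change score gains nothing over the 12-month score alone, and at r = 0.3 it is worse.

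**The case against.** The strongest reply is that the documents never say that the scales are left out of the baseline survey. The section 5.1 sentence is about when impact is assessed. The same section lists the primary outcomes as measured at 5 and 12 months without naming baseline, yet EPIC is taken at baseline. Survey content is left to the study team to finalise. This stands in part: the absence of a baseline is an inference. It is still the natural reading, because section 5.5 supplies the baseline for EPIC and nothing does so for these two scales.

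Three stronger conclusions are tempting and are not supported.

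- *The comparison is biased or unprotected.* Randomisation makes it unbiased in expectation. Site, treatment type, baseline EPIC and PEPPI scores, and record data are available for partial adjustment and for describing drop-outs. Only the scales' own baseline is missing. With about 28% lost, a completers' analysis still needs an assumption about drop-out, but a baseline score would inform that assumption, not remove it.
- *The tests are underpowered.* At the plan's 0.33 SD and two-sided 0.05, power is already about 91%. A smaller effect makes the test look weak (0.25 SD gives 70% unadjusted and 82% at r = 0.5), but 0.25 SD appears nowhere in the plan.
- *Section 5.6 contradicts itself.* Its sentence on other outcomes gives self-management implementation and confidence as examples, not these two. The gap is an unspecified model, not a contradiction.

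It is also fair that the outcomes are secondary and that a 12-month-only comparison is a legitimate design.

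**Conclusion.** The point holds as a minor, worthwhile improvement. As most naturally read, the plan takes no baseline score for the VR-12 or perceived cancer control, and its rationale does not explain why. The comparison remains unbiased in expectation and adequately powered for 0.33 SD at two-sided 0.05. The loss is one of efficiency (a standard error that could be about 5% to 29% smaller, 13% at r = 0.5), of adjustment for chance imbalance on these scales, and of the means to examine drop-out by starting level on them.

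The size rests on an assumed correlation of 0.3 to 0.7, since the plan's 0.5 refers to symptom scores only, and on 397 completers. If the scales are in fact in the baseline survey, what remains is to say so and to specify how the scores will be used.

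**What to change.** State in sections 5.1 and 5.5 whether the two scales are in the baseline survey. If they are not, add the VR-12 and the cancer-control items, or at least the VR-12, to the existing pre-randomisation telephone survey. In section 5.6, specify analysis of covariance of each 12-month score with its own baseline as covariate, not a change score, and state the significance level for these two outcomes.

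The cost is a slightly longer baseline call, with no extra contact. How much longer cannot be read from the documents, which do not give the number of cancer-control items. Baseline already includes a screener, a survey and a separate automated EPIC call, which is why the VR-12 alone is a reasonable minimum.

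If enrolment is too advanced to add items, adjust the 12-month model for baseline EPIC and PEPPI scores, site and treatment type. This recovers part of the precision at no data-collection cost. Section 5.5 places the automated EPIC call after the baseline survey without saying whether it precedes randomisation; confirm that it does before using EPIC as a baseline covariate.

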5.2 Recruitment Methods

- **State how many subjects will be needed.**

Veteran participants:

We estimate as many as 553 - 650 veterans will be randomized.

VA employees:

We plan to interview up to 40 key stakeholders (up to 4 PCPs and 4 specialists at each site, plus interviews of stakeholders at the VISN and national level), recruited and interviewed by AAVA project staff.

- **Describe when, where, how and by whom potential subjects will be identified and recruited.**

RCT:

Recruitment and informed consent. We have been granted a waiver of documentation of informed consent and HIPAA Authorization. Potential participants will be sent an introductory letter and a patient information sheet. The introductory letter will briefly describe the study and include a local or toll free number to call if the patient is not interested in participating or would like more information. After one week, a study coordinator will telephone those Veterans who did not opt-out, and if the patient is interested, the coordinator will ensure the patient is properly informed, obtain verbal informed consent, administer the Brief Screener by phone and determine whether that Veteran meets the criteria of having a clinically meaningful symptom burden score (1 or higher on any one symptom, as a measure of low function or high symptom burden) on at least one item.

For Veterans with significant symptoms, the coordinator will assess interest in participating in the trial, review the patient information sheet and answer any questions. The patient information sheet will clearly state that being in the study means that some Veterans will be enrolled into a program of weekly automated telephone calls plus newsletters while the other group will receive only written information about PC symptom self-management at one time-point. We will make clear that we are studying these methods for helping Veterans with long term PC symptoms and we do not have evidence that one approach is better than the other. The patient information sheet will not state which of these is the "intervention" arm. It will further state that to be in the study requires that the Veteran's name, address, telephone number, age, ethnicity, marital/relationship status, prostate cancer treatment type, initial diagnosis date, service branch VA Site and survey scores be entered into a secure website to a server that meets all VA criteria for confidential data transfer, but that this will be done by the study coordinator and not by the Veteran himself. Finally, the patient information sheet will inform the participant that he is agreeing to a baseline survey and follow up phone call at 5- and 12-months following enrollment. After each of these three assessments, both intervention and control group patients will be called by the IVR system for standardized administration of the EPIC.

Once the Veteran has been deemed eligible, the information sheet has been reviewed, all questions have been answered, and the patient has verbally consented to participate, the study coordinator will then administer the baseline survey over the telephone. Once a participant has been enrolled into the study, AAVA staff will send a \$10 gift card by mail.

Should the phone number or address obtained from CDW turn out to be incorrect or outdated, study staff will check the patient's medical record for current contact information. In the event a letter is returned to us in the mail and an updated address is not available, study staff will attempt to contact the patient by phone up to 3 times including

leaving messages. If the patient is agreeable, study staff will send the recruitment letter to the patient's updated address and contact the patient again after one week to complete the recruitment call as described above.

Process Evaluation:

At the end of the intervention delivery phase, the research team will conduct semi-structured interviews with up to 40 key stakeholders (up to 4 PCPs and 4 specialists at each site, plus interviews of stakeholders at the VISN and national level). Drs. [name] and [name] will arrange interviews with up to 4 PCPs at each site (with the support of the primary care service director) and 4 specialists providing PC survivorship care per site. Recruitment of these individuals will be done via email and phone, with introductory letters sent by [name] and the site PIs. Guided interviews will be conducted with these physicians in person or by telephone to assess perceptions of system factors contributing to positive intervention outcomes, and will be audiotaped with their verbal consent.

To identify participant factors influencing intervention effectiveness, we will re-contact participants in the intervention arm who achieved the best outcomes (i.e., had the highest reduction in symptom burden over the study period) and the worst outcomes (i.e., no change in symptom burden or increase in symptom burden). Starting in month 9 of year 3, we will contact 5 participants at each site in the best outcome group, and 5 participants per site in the worst outcome group (N=40 total), based on preliminary data analyses available at that time. We will conduct in-depth interviews with these participants by telephone to determine patient perceptions and factors associated with the intervention's effectiveness. Participants in these interviews will be limited to patients who agreed to this interview during the 12-month follow-up survey. We will initiate re-contact during month 9 of year 3, and continue into months 1-2 of year 4. Telephone interviews are expected to take 30-40 minutes and will be audiotaped with the participants' verbal consent.

- **Describe materials that will be used to recruit subjects, e.g., advertisements. Include materials as an appendix or separate attachment.**

Potential participants will be sent an introductory letter and a patient information sheet. The letter will describe the study and include either a toll-free or local number to call if the patient is not interested in participating or would like more information.

- **Describe any payments to subjects, including the amount, timing (at the end of the study or pro-rated for partial study participation), method (e.g., cash, check, gift card), and whether subjects will experience a delay in receiving the payment.**

Once a participant has been enrolled into the study, AAVA staff will send a \$10 gift card by mail. Those patients participating in the evaluation process will receive an additional \$20 to compensate them for the 30-40 minutes required for the interview. Payments will not be pro-rated as all payments for this project are minimal and made on a one-time basis. Payment for the ~40 patients participating in the process evaluation interviews will also be in the form of a gift card and will be sent by the AAVA project staff once the interview has been completed.

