5.5 Study Evaluations

- **Describe all evaluations to be conducted (including screening; tests/questionnaires that will be administered; any procedures that subjects will be required to complete) and data collection methods. Include materials as an appendix or separate attachment.**

Potential participants will be sent an introductory packet from the AAVA. After one week, the coordinator will telephone those Veterans who did not opt-out, and if the patient is interested, the coordinator will administer the Brief Screener by phone and determine whether that Veteran meets the criteria of having a clinically meaningful symptom burden score (1 or higher on any one symptom, as a measure of low function or high symptom burden) on at least one item. Once the Veteran has been deemed eligible and the baseline survey has been administered, the veteran will be randomized to the automated telephone system or enhanced usual care (information about self-management).

Veterans randomized to the automated telephone system intervention will receive 4 automated phone calls over a 3-month period: 1 at study start and then once a month for 3 months. These calls will last approximately 15 minutes and will include questions about symptoms, will allow the veteran to identify a goal to work on, and help the veteran take steps towards reaching their goal and managing their symptoms. At the end of each call, the veteran will also have the option of listening to an audio testimonial tailored on priority symptom area. Following each call, the veteran will receive a personalized newsletter that will provide more details regarding their symptoms and strategies to help them manage their symptoms. Each newsletter will be 4 – 8 pages in length. The automated system will try to reach the veteran up to eight times over the course of 4 days (see IVR call schedule). If the veteran has not completed the call by day 3 of the call window, study staff will make up to 5 or 6 attempts to contact the patient (including leaving messages) to verify the phone number and preferred call time. If the veteran has still not completed the call by day 5 of the call window, study staff will again make up to 5 or 6 attempts to contact the patient. Following each reminder call, study staff have the option to initiate additional IVR calls should veteran be agreeable.

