Telephone surveys of both intervention and control groups to obtain baseline and follow-up measures will be conducted at three time points: baseline, five months, and 12 months post-enrollment. Hard copies of follow-up surveys will be sent to any participants expressing preference for completing the survey by paper and participants we are unable to reach by phone. Survey content will be finalized by our study team using established approaches during year 1 and pilot tested among prostate cancer survivors affiliated with the VAAHS prior to use in the trial. Each survey will be administered by the VA coordinator over the telephone. After each of these three assessments, both intervention and control group patients will be called by the IVR system for standardized administration of the EPIC. Baseline surveys will be done prior to randomization. Beginning approximately 4 months following enrollment, initial attempts will be made by the coordinating team to contact the participant by phone to complete the Time 2 survey, and approximately 11 months following enrollment to complete the Time 3 survey. For all 3 surveys, up to 5 or 6 attempts will be made to complete the survey, including leaving voice mails and providing call-back information for participants who are not home. Times to complete the surveys will be scheduled as desired by participants. Finally, if participants are unable or unwilling to complete the survey by telephone, a paper-and-pencil survey will be mailed to them with a return envelope. Participants who fail to return the paper survey within one month may be sent a second paper survey by mail. In addition, a reminder newsletter will be sent to participants 1-2 months prior to their expected 12-month follow-up. All participants completing the 12-month assessment will be sent an "early results" newsletter showing some preliminary survey results and thanking participants for their contribution to the study.

Patients are free to skip any survey questions administered by study staff that they would prefer not to answer. However, because the newsletters are tailored based on responses to questions administered by the automated telephone system, these questions are not optional. Nevertheless, patients are free to hang up the phone if they prefer not to complete an IVR call. Patients will also have the option to call into the IVR system using a toll free number if they prefer not to wait to complete their call.

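### Section 5.2 has the information sheet describe weekly automated calls, whereas Section 5.5 specifies four calls over three months; the two must be reconciled

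*Combined protocol and SAP*

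**What the plan says.** In Section 5.2 the protocol sets out what the information sheet must contain: that some men will be "enrolled into a program of weekly automated telephone calls plus newsletters", while the other men receive written material once. No number of calls and no length of programme is given there. The sheet is mailed with the introductory letter about a week before the coordinator telephones, and it is gone over again on the telephone. The baseline survey follows once "the information sheet has been reviewed, all questions have been answered, and the patient has verbally consented to participate".

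Section 5.5 describes delivery. Men in the intervention arm "will receive 4 automated phone calls over a 3-month period: 1 at study start and then once a month for 3 months". On length it says "These calls will last approximately 15 minutes", and on newsletters "Following each call, the veteran will receive a personalized newsletter". It refers to a separate IVR call schedule, which is not among the documents.

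**The concern.** A weekly programme and one with a call at the start and then one a month cannot be the same programme. One statement governs what men are to be told before they agree, and the other governs what the system is to deliver.

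Call frequency is the main burden of the intervention arm, and consent is verbal with documentation waived, so the mailed sheet matters as a written account of what is being agreed to. It also arrives together with an opt-out number. A man put off by the prospect of weekly calls could decline before a coordinator has spoken to him. What is at stake is the accuracy of consent, possibly the make-up of the enrolled sample, and a protocol that specifies its own intervention only once.

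**Working it through.** **Inputs**

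- Frequency to be stated to participants: weekly, with no duration or count (Section 5.2).
- Frequency to be delivered: one call at the start, then one a month for three months (Section 5.5).
- Length of a call: about 15 minutes (Section 5.5, given for the delivered calls only).
- Newsletters: one after each call (Section 5.5).

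**The plan's own figure.** 1 + (1 per month × 3 months) = 4 calls, which reproduces the four stated in Section 5.5. Time on calls: 4 × 15 = 60 minutes.

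**Could another feature of the plan explain the weekly figure?**

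- Redials. "The automated system will try to reach the veteran up to eight times over the course of 4 days": these are attempts to complete one scheduled call, not further calls.
- Outcome calls. "After each of these three assessments, both intervention and control group patients will be called by the IVR system for standardized administration of the EPIC": these go to both arms and are not the intervention. Adding them gives 4 + 3 = 7 automated calls over 12 months, which is still not weekly.
- The study team's own conference calls in Section 8.0 are described as roughly weekly, but they do not involve participants.
- Section 5.1 describes the intervention without giving a frequency.

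None of these reconciles the two sections.

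**Size of the gap.** Section 5.2 gives no duration, so the duration has to be assumed. The 15-minute length is also borrowed from Section 5.5. Calls = number of weeks (plus one if a separate start call is counted); minutes = calls × 15; ratio = calls ÷ 4.

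| Assumed weekly programme | Calls | Minutes | Ratio to Section 5.5 |
|---|---|---|---|
| 4 weeks | 4 | 60 | 4 ÷ 4 = 1.0 |
| 3 months, about 13 weeks | 13 | 195 | 13 ÷ 4 = 3.25 |
| 3 months plus a start call | 14 | 210 | 14 ÷ 4 = 3.5 |

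If a newsletter follows every call, the newsletter count changes in the same ratio. At four weeks the totals agree, but the spacing and the length of the programme still do not.

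**Effect on the statistics.** Call frequency is not an input to the sample size or the alpha in Section 5.6. The Aim 1 models there compare the groups through an indicator for intervention group, not through calls received. Consent and the baseline survey come before randomisation, so a misdescription in the sheet would reach future members of both arms alike.

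**The case against.** The strongest reply is that Section 5.2 is protocol prose about the sheet, not the sheet itself. The sheet and the recruitment script are not among the documents, and the sheet as issued may already carry the Section 5.5 schedule. A reader might infer that men are in fact consenting to a programme other than the one delivered. The documents do not show that. They show only that this would follow if the sheet says what Section 5.2 requires.

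Three further inferences should also be resisted.

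- That the burden is misstated threefold. This figure depends on carrying the three-month duration from Section 5.5 into Section 5.2. A shorter weekly programme would narrow the difference.
- That the final report could not say what was tested. Section 5.5 describes delivery in detail, and data from the automated system are downloaded and linked by study ID, so the calls delivered should be reportable.
- That the classification of adherence is compromised. The documents contain no adherence definition, per-protocol set or dose analysis, and missed calls are followed up within each call window.

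These points limit the consequences. They do not remove the conflict: both statements are current text, and a team that followed the protocol to the letter would tell men one frequency and deliver another.

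**Conclusion.** The point holds as an internal inconsistency: the protocol is wrong as written, because it gives two different call frequencies for one intervention and one of them is prescribed for consent-facing text. That conclusion rests on the protocol wording alone.

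The consequence for participants is conditional. If the sheet follows Section 5.2, men would be told a call burden different from the one delivered, with possible effects on informed consent and on willingness to enrol, before allocation and so for both arms. The size cannot be fixed from the documents: it runs from no difference in total calls (a four-week weekly programme) to about 3.25 to 3.5 times as many (weekly over three months), with 15 minutes a call assumed throughout. Sample size, alpha and the between-group comparison stand as they are. This should be corrected, but it does not threaten the trial's validity.

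**What to change.** Reconcile Sections 5.2 and 5.5 so that the protocol states one call schedule, giving the frequency, number of calls and duration in both places. Then check the information sheet, the recruitment script and the IVR call schedule against it, and correct any that differ. The documents do not settle which frequency is intended, so the study team must say, and none is recommended here.

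The cost is a wording amendment to the protocol and, if the sheet or script turns out to differ, to those as well. No change to the design, sample size or analysis is needed.
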